6.1.7 Prior and Concomitant Anti-cancer Therapy and Procedures

The prior anti-cancer therapy and procedures are recorded on the eCRFs Diagnostic and Therapeutic Procedures (Prior) for iNHL, Systemic Anti-Cancer Therapy (Prior) and Radiotherapy (Prior). The concomitant anti-cancer therapy and procedures are recorded on the eCRFs Diagnostic and Therapeutic Procedures (Concurrent) for iNHL, Systemic Anti-Cancer Therapy (during Follow-Up) and Radiotherapy (during Follow-Up).

The minimum, median, and maximum number of prior systemic anti-cancer therapy lines as well as number of patients with 1, 2, 3, ≥ 4 lines of therapy will be summarized by treatment group for FAS. Time since last systemic anti-cancer therapy will be summarized using descriptive statistics by treatment group for FAS. The time between the start day of last course of systemic anti-cancer therapy and the day of confirmation of the most recent

Statistical Analysis Plan

BAY 80-6946 / 17322

Page: 13 of 20:

progression will also be displayed as a classification table, showing proportions of patients with \leq 6 months vs. > 6 to < 12 months vs. ≥ 12 months, by treatment group.

The following anti-cancer therapy will be summarized by treatment group for FAS:

- prior and concurrent diagnostic and therapeutic procedure
- prior and follow-up radiotherapy
- prior and follow-up systemic therapy

6.1.8 Study Drug Administration

Descriptive statistical summaries of study drug exposure will be provided for the following variables:

- Overall extent of exposure (OEE) in days:

Defined as the time from the first administration of the first study treatment (day_{first}) until the last administration of the last study treatment (day_{last}), including 7 additional days in order to consider the weekly dosing regimen, is calculated as:

$$\text{OEE (days)} = \text{day}_{\text{last}} - \text{day}_{\text{first}} + 7.$$

- Number of cycles
- Number of infusions during treatment phase and categorized by 1-6, 7-12, 13-18 and etc.
- Total dose actually administered (mg)

OEE will include interruptions/delays during treatment. As a general rule, and in accordance with the Therapeutic Area Standard oncology team and the timing concept, trailing “0 mg” records (not followed by any positive amount of drug), will not be included in the calculation of any drug duration or amount. Similarly, the according trailing “drug interruptions” will not be used in statistical tables. A footnote will be included, stating that “Interruption becoming permanent study treatment discontinuation before resumption of study treatment is not accounted as an interruption”.

For patients with dose modification, the total number (%) of subjects with dose reductions, interruptions/delays, re-escalations and the total number (%) of dose reductions, interruptions/delays, re-escalations and the reasons will be summarized. Number of reduction, interruption/delay and re-escalation per subject will also be summarized.

6.2 Efficacy

Due to the limited number of patients enrolled in this study, the study efficacy objectives and analyses were removed and the tumor assessment was stopped to be collected since 01 DEC 2017. Summary of tumor response by investigators' assessment will be provided. Progression-free survival and best overall response will also be listed.

Best overall response (BOR)

BOR is defined as the best response per Cheson criteria (ordered CR, PR, SD, PD, NE) and per Owen criteria (ordered CR, very good partial response (VGPR), PR, Minor response(MR),

Statistical Analysis Plan

BAY 80-6946 / 17322

Page: 14 of 20:

SD, PD, NE) over all post-treatment assessments on or prior to the first progression. Tumor assessments after first PD and after start of new anticancer therapy are not considered for best overall response.

Objective response rate (ORR)

ORR is assessed in all patients up to the time of analysis of PFS. ORR is defined as the proportion of patients who have a best response rating over the whole duration of the study (i.e. until time of analysis of PFS) of complete response (CR) or partial response (PR) according to Cheson criteria Lugano Classification and for patients with WM a response rating of CR, very good partial response (VGPR), PR, or minor response (MR) according to Owen Criteria.

Progression-free survival (PFS)

For patients who were randomized to copanlisib until the end of the study and who were randomized to placebo until switching to copanlisib after PD or after unblinding, PFS is defined as the time (in months) from the randomization date to first disease progression or death due to any cause, if death occurs before progression is documented.

For patients who switched from placebo to copanlisib, PFS is defined as the time (in months) from the start date of copanlisib to first disease or death due to any cause, if death occurs before progression is documented.

For details for radiological tumor assessments see protocol section 7.3.2 and for details for tumor assessments in patients with WM see protocol section 7.3.3.

PFS for patients without PD or death at the time of analysis will be censored at the last actual date of tumor assessment or last biochemical assessment for patients with WM without lesions evaluable by imaging.

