4.5 Data Rules

If time intervals are to be displayed other than days in statistical evaluations, then one year is considered to have 365.25 days (average length of a year, including leap years), one month is considered to have 30.44 days (average length of a month, including leap years), one week is considered to have 7 days, and one cycle is considered to have 28 days (i.e. 4 weeks).

Baseline

Baseline is defined as the last available measurement performed prior to the first dose of Copanlisib/placebo study drug administration at Cycle 1 Day 1 for the patients who initially received Copanlisib/placebo. For the patients who initially received placebo and switched to Copanlisib after unblinding, baseline is defined as the last available measurement prior to the first dose of Copanlisib after switching.

Repeated measures

Statistical Analysis Plan

BAY 80-6946 / 17322

Page: 10 of 20:

If there are repeated measurements per time point (e.g. laboratory values, vital signs, etc.), the following rules will be used (unless otherwise specified):

- Before the start of the study drug administration (i.e., for screening and baseline value), the latest measurement at scheduled visits will be used. Unscheduled visits will be used, if there are no measurements at pre-baseline or baseline scheduled visits. If the latter is the case, the last unscheduled visit will be used.
- In case of repeated measurements at any post-baseline time point, the first value of the scheduled measurements at that time point will be used. No unscheduled measurements will be used for any time points besides screening / baseline even when measurements at scheduled visits are missing.

5. Analysis Sets

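### For patients who switch from placebo to copanlisib, the best overall response rule (section 6.2) and the baseline rule (section 4.5) do not fit the separate switcher summaries in section 6

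*SAP*

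**What the plan says.** Section 6 of the SAP defines a copanlisib group and a placebo group. The placebo group ends at the switch, which may follow progression (PD) or unblinding. The section then asks for efficacy and safety to be summarized separately for the switchers. Section 3 (Treatment Period) describes both routes: a placebo patient with PD before the unblinding cut-off may choose to switch, and a patient still on placebo at unblinding switches afterwards.

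Section 6.2 plans a summary of investigator-assessed tumor response, and states "Progression-free survival and best overall response will also be listed". It defines best overall response (BOR) as the best rating "over all post-treatment assessments on or prior to the first progression", and adds "Tumor assessments after first PD and after start of new anticancer therapy are not considered for best overall response". There is no separate BOR rule for switchers. The only efficacy rule specific to them is that progression-free survival (PFS) runs "from the start date of copanlisib to first disease or death due to any cause".

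Section 4.5 sets the general baseline before the first study drug dose at Cycle 1 Day 1, with one exception: "For the patients who initially received placebo and switched to Copanlisib after unblinding, baseline is defined as the last available measurement" before the first copanlisib dose after switching. Section 6.3.1, by contrast, restarts treatment-emergent adverse events at the first copanlisib dose for all switchers, whichever route they took.

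**The concern.** The switcher group exists to show what happened on copanlisib. Two rules can put placebo-period information into it, or keep copanlisib-period information out.

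- **Response.** The BOR window closes at the first PD. For a patient who switched because of PD, that happens before the first copanlisib dose, so a response on copanlisib cannot be recorded. For a switcher without PD, nothing opens the window at the switch, so a rating obtained on placebo can become the switcher's BOR and count in the objective response rate (ORR).
- **Baseline.** A patient who switched after PD falls outside the section 4.5 exception and keeps the pre-placebo value. In the switcher tables, change from baseline then spans the placebo period as well as copanlisib, while the same patient's adverse events are counted from copanlisib only.

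At stake are the accuracy of the switcher response summary and BOR listing, and the consistency of the switcher safety tables. Safety is the study's only remaining objective, so the baseline gap reaches further than the response gap.

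**Working it through.** The SAP states no figure on this point, so there is none to reproduce. The check compares the rules and applies them to assumed patients.

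**Step 1: which rules restart at the first copanlisib dose?**

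| Rule | Switch after PD | Switch after unblinding |
|---|---|---|
| Adverse events (6.3.1) | restarts | restarts |
| PFS origin (6.2) | restarts | restarts |
| Baseline (4.5) | not reset | reset |
| BOR window (6.2) | no restart stated | no restart stated |

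**Step 2: BOR under two derivations.** The inputs are assumed rating sequences, ordered as in section 6.2 (CR, PR, SD, PD, NE).

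- As written: the best of all ratings up to and including the first PD in either period.
- By period: the best copanlisib rating up to the first PD on copanlisib, or NE if there is none.

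| Placebo ratings | Copanlisib ratings | As written | By period |
|---|---|---|---|
| SD, PD | PR | SD | PR |
| PD | CR | PD | CR |
| PR, PD | SD, PD | PR | SD |
| PR | SD, PD | PR | SD |
| SD, SD | none | SD | NE |
| SD, PD | none | SD | NE |

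In the first two rows a copanlisib responder is shown as a non-responder. In the next two a placebo response is credited to the switcher group. In the last two a placebo rating stands where nothing was assessed on copanlisib. The error can go in either direction. These sequences show what the rule does, not how often it happens.

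**Step 3: where baseline enters.** Section 6.3.3 plans laboratory changes from baseline and worst-grade shifts. Section 6.3.4 groups patients by baseline HbA1c (below 5.7%, 5.7% to below 6.5%, 6.5% or more) and tabulates shifts to end of treatment. Section 6.3.5 plans vital-sign changes. Take an assumed patient who switched after PD, with HbA1c below 5.7% before placebo, in the middle band before copanlisib, and at 6.5% or more at end of treatment. With the retained baseline the table shows a shift from the lowest band to the highest. With the reset baseline it shows a shift from the middle band to the highest.

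**Step 4: a conditional side point on PFS censoring.** An event-free patient "will be censored at the last actual date of tumor assessment", with no requirement that this date follow copanlisib start. PFS in months = (censoring date − copanlisib start) / 30.44, using the month length in section 4.5. If the last assessment came 7, 28 or 84 days before copanlisib start (assumed gaps):

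- −7 / 30.44 = −0.23 months
- −28 / 30.44 = −0.92 months
- −84 / 30.44 = −2.76 months

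This can arise only if an event-free switcher had no assessment after the switch. Section 6.2 says "the tumor assessment was stopped to be collected since 01 DEC 2017", which makes that possible, but the SAP gives no switch dates.

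**The case against.** The strongest reply is that the period structure is already in the SAP and any programmer would apply it. Section 6 ends the placebo group at the switch. Section 3 says that, after individual unblinding, placebo patients who switch have their assessments reset as though they were starting again at Cycle 1 Day 1. This shows what was probably intended. But the section 3 reset concerns the visit schedule and does not define a BOR window, and section 6.2 excludes assessments after first PD without qualification. Where the authors wanted an analysis clock to restart, they said so.

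On baseline, one could read unblinding in section 4.5 broadly enough to cover the PD route. Sections 6, 6.2, 6.3.1 and 7 tell against this, because each names PD and unblinding as alternative routes.

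The objection does succeed against several stronger readings that a reader might infer:

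- **That PFS events fail to restart.** A time from copanlisib start to a first event ordinarily means the first event after that start. The word missing after disease in the switcher sentence is clerical, since the same sentence goes on to mention progression.
- **That the ORR window is a separate defect.** The wording "best response rating over the whole duration of the study (i.e. until time of analysis of PFS" reads as a data cut-off, and ORR is built on the best response, so correcting BOR corrects ORR.
- **That the retained baseline distorts response ratings.** The SAP does not link the section 4.5 baseline to investigator-assessed response, leaves tumor assessment detail to the protocol, and names no table of tumor-size change.

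**Conclusion.** Two rules are wrong as written for the switcher summaries: the BOR exclusion after first PD, and the baseline reset limited to switches after unblinding. Severity is low. Efficacy objectives were removed, all outputs are descriptive and no test depends on them. The number of patients affected cannot be given, because the SAP states neither a count of switchers nor their switch dates; if nobody switched after PD, the baseline gap has no effect. Every rating sequence, HbA1c path and date gap shown above is assumed. The conclusion rests on the SAP wording alone, and existing programs may already follow the period-based reading.

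**What to change.** **Section 6.2.**

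- For switchers, derive BOR only from assessments after the first copanlisib dose, up to the first later PD or the start of new anticancer therapy. Report NE if there are none. State that the switch to copanlisib does not itself count as new anticancer therapy for this purpose.
- For the placebo group, use assessments up to the first copanlisib dose.
- Define ORR from this period-specific BOR.

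**Section 4.5.** Apply the reset baseline to all switchers, after PD as well as after unblinding.

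**Minor tidying of the PFS text.** In the switcher sentence, name the event as first disease progression or death after copanlisib start. Censor event-free switchers with no post-switch assessment at copanlisib start; this matters only if such patients exist.

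**Cost.** A few sentences in section 6.2 and one in section 4.5, plus a check of the BOR, ORR, PFS and baseline programs, with changes where they follow the literal text. No new data are needed. The downside is that some switchers may become NE, leaving fewer evaluable for response in an already small group.

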The start of the treatment period is defined by first administration of study drug (Copanlisib or placebo). Copanlisib will be administered IV over approximately 1h at starting dose of 60 mg on Days 1, 8 and 15 of each 28-day treatment cycle. Treatment will be continued until progressive disease (PD) by radiological assessments or clinical progression (tumor evaluations will be made at intervals that comply with the institution's standard of care [per investigator's assessment]), unacceptable toxicity, or until another criterion is met for withdrawal from the study treatment. Before unblinding, patients in the placebo arm will receive a placebo IV infusion at the same schedule as that of Copanlisib arm. However, when placebo patients had PD before unblinding cut-off, they can choose to switch to Copanlisib and continue to stay in the study.

Disease progression (PD) defined in the Lugano Classification (3) and the Owen criteria (4) for patients with WM will be assessed.

Statistical Analysis Plan

BAY 80-6946 / 17322

Page: 8 of 20:

All patients, after unblinding procedures are completed, will be offered an opportunity to continue this clinical study and receive active treatment with Copanlisib. Patients who are on Copanlisib treatment at the time of unblinding will continue Copanlisib treatment. Patients who are on placebo at the time of unblinding will switch to Copanlisib treatment after unblinding procedures are completed. After individual patient unblinding, patients receiving placebo, who switch to Copanlisib will have all study assessments reset to the initial schedule of study evaluations (i.e. as if the patient was restarted the study at Cycle 1 Day 1).

An End-of-treatment (EOT) visit will be performed within 7 days after the decision is made to discontinue study treatment.

Safety Follow-up Period

Following completion of the EOT visit, patients will enter the Safety follow-up. The Safety follow-up (SFU) visit will take place 30 days (window of +5 days allowed) after the last administration of study drug.

All patients who have already completed the safety follow-up visit at the time the amendment 6 becomes effective will discontinue the study.

4. General Statistical Considerations

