5.1 Assignment of analysis sets

Full analysis set (FAS)

All patients who were randomized to treatment arms at the start of the study will be included in the FAS. Protocol deviation, demographics, baseline characteristics, medical history, prior and concomitant medication, prior and concomitant anti-cancer therapy will be summarized in the FAS.

Safety analysis set (SAF)

All patients with at least one administration of study drug will be included in the SAF. The SAF will be used for the analyses of study drug exposure, safety and efficacy variables.

All patients with valid pharmacokinetic (PK) data may be analyzed in the evaluation of PK concentrations and parameters.

Patients who signed the informed consent but were not assigned to treatment will be considered screening failures. They will be listed separately.

6. Statistical Methodology

Disposition, protocol deviations, demographics, baseline cancer characteristics, medical history, prior and concomitant medication, prior and concomitant anti-cancer therapy, drug exposure, efficacy and safety variables will be summarized separately for 2 groups including patients

- who were randomized to copanlisib until the end of study (copanlisib group)
- who were randomized to placebo until switching from placebo to copanlisib after PD or after unblinding (placebo group)

Disposition, protocol deviations, concomitant medication, concomitant anti-cancer therapy, drug exposure, efficacy and safety variables will also be summarized separately for patients who switched from placebo to copanlisib.

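### SAP section 6.2 gives ORR a wider assessment window than BOR, so ORR can count responses seen after progression or on later therapy

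*SAP*

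**What the plan says.** Section 6.2 defines the two response measures one after the other.

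- **BOR** is the best rating "over all post-treatment assessments on or prior to the first progression". A second sentence adds: "Tumor assessments after first PD and after start of new anticancer therapy are not considered for best overall response".
- **ORR** opens with "ORR is assessed in all patients up to the time of analysis of PFS" and continues: "ORR is defined as the proportion of patients who have a best response rating over the whole duration of the study". A bracket then equates that duration with the time of the PFS analysis. The responding categories are CR or PR under Lugano, and CR, VGPR, PR or MR under Owen for WM.

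The opening text of section 6 sets the reporting groups for efficacy and safety. One covers patients "who were randomized to copanlisib until the end of study (copanlisib group"). The other covers patients "who were randomized to placebo until switching from placebo to copanlisib after PD or after unblinding (placebo group"). Patients who switched are also summarized on their own.

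Section 6.2 further says that the efficacy objectives were removed, that tumor assessments were no longer collected from 01 DEC 2017, that tumor response by investigator assessment will be summarized, and that PFS and BOR will be listed.

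**The concern.** ORR is normally the share of patients whose BOR is a response. Here it has its own window, limited by a study-level time and not by the patient's own progression or next therapy. A programmer who follows each sentence as written can derive two responder counts from the same data.

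Two things are at stake. The response summary and the BOR listing could disagree for the same patients. And ORR could credit a group with a response that came after study treatment had failed, or that belongs to a different treatment.

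**Working it through.** The SAP states no figure for ORR, sample size or power, so there is nothing to reproduce. The check sets the definitions side by side and then works out the size of a discrepancy.

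**Step 1. Compare the windows (section 6.2).**

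| | BOR | ORR |
|---|---|---|
| Stops at first PD | yes | not stated |
| Stops at new anticancer therapy | yes | not stated |
| Latest limit | the patient's own PD or new therapy | time of the PFS analysis, for all patients |
| Refers to the other definition | – | no |

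**Step 2. Direction.** For a given patient and a given starting point, the BOR window lies inside the ORR window. A best rating over a larger set of assessments cannot be worse, so literal ORR is at least as high as the BOR-based rate.

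**Step 3. Can the two differ in each group?**

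- *Copanlisib group.* Its period runs to the end of study, so the group definition does not supply the missing cut. Take a patient with SD, then PD, then PR on another regimen before the PFS analysis. BOR is SD, but the patient meets the ORR definition. The same holds for SD, a stop without PD, a new regimen, then PR.
- *Placebo group.* Section 3 says that "when placebo patients had PD before unblinding cut-off, they can choose to switch to Copanlisib and continue to stay in the study". A response after that switch falls outside the placebo group, because section 6 ends the group at the switch. If that cut is applied, this route is closed.
- *Switched group.* The post-switch period has no stated cut at PD or new therapy for ORR, so the exposure is the same as in the copanlisib group. PFS in section 6.2 is defined separately for the post-switch period; BOR and ORR are not.

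Section 6.1.7 shows that later therapy is recorded, on the forms "Systemic Anti-Cancer Therapy (during Follow-Up) and Radiotherapy (during Follow-Up"). It does not show that tumor response to that therapy was assessed.

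**Step 4. Size.** Let n be the group size. Let k be the number of patients with no responding rating inside the BOR window but one inside the ORR window. Then:

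ORR (literal) − ORR (from BOR) = k / n

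The SAP gives neither n nor k. With k = 1 and assumed n:

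- n = 5: 1/5 = 20 percentage points
- n = 10: 1/10 = 10 percentage points
- n = 20: 1/20 = 5 percentage points

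**The case against.** The strongest reply is that the two texts can be reconciled. ORR follows BOR directly and speaks of a best response rating. The whole-study wording could be meant as a calendar data cut, with the BOR exclusions still deciding which assessments count. That may well have been the intent. But the sentence does not say so, and the only window it states is the wider one.

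Four further points limit the concern, and they stand.

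- **Reachability.** The discrepancy needs tumor assessments after PD or after new therapy. Recorded follow-up therapy, and the active follow-up phase named in section 6.1.1, do not prove that these were collected. The BOR exclusion suggests that the authors thought them possible, though it may be standard wording.
- **Data stop.** Tumor data collection ended on 01 DEC 2017. A reader might infer that the ORR window is open-ended because no date is given for the PFS analysis. That goes too far: the data stop bounds what can enter, and section 7 replaces the protocol's two cut-offs with a simplified analysis.
- **Crossover.** A reader might also infer that responses on copanlisib inflate the placebo ORR. The section 6 cut at the switch does not support that.
- **Use.** Safety is the only objective stated in section 2, and section 4.1 confines the analyses to descriptive statistics. ORR is not named among the outputs announced at the start of section 6.2, and the BOR listing would expose a mismatch patient by patient. No test or error rate depends on ORR.

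**Conclusion.** The inconsistency is real. ORR and BOR have different windows as written, and literal ORR can exceed the BOR-based responder rate in the copanlisib and switched groups by counting responses after PD or to later therapy.

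The consequence is limited. It affects a descriptive measure in a study whose efficacy objectives were removed. It is 1/n per affected patient: 5 to 20 percentage points for one patient, if groups hold 20 down to 5. Those sizes are assumptions, and the documents do not show that any such patient exists. They therefore do not support a claim that the reported ORR will be inflated, only that the definition allows it. The point is still worth correcting: one stated rule conflicts with the rule beside it, section 6 still has efficacy variables summarized by group, and the repair is short.

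**What to change.** In section 6.2, delete the clause that sets the ORR window to the whole study up to the PFS analysis, and define ORR from BOR. Suggested content:

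- ORR is the proportion of patients whose BOR is CR or PR (Lugano), or CR, VGPR, PR or MR (Owen, for WM).
- BOR is derived within each section 6 analysis period: randomized copanlisib; placebo until the switch; copanlisib after the switch.
- In each period, only assessments up to the first PD in that period, and before any new non-study anticancer therapy, count.
- For the post-switch period, only assessments after the first copanlisib dose count.

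The reset by period is needed. Placebo patients who switched after PD already have a first PD on record. Tying ORR to BOR without the reset would discard all their post-switch assessments and make them non-responders by construction. The reset also matches how section 6.2 already starts PFS afresh for switched patients.

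The cost is about one sentence of SAP text and no new data. ORR may be slightly lower than under the present wording.
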